#### Pregnancy Test

As described in Table 1 and Section 4.4, a urine or serum pregnancy test should be collected for all females of childbearing potential prior to study drug initiation, and if pregnancy is suspected. If not possible to collect pre-dose, then collect as soon as possible after study drug initiation. It is at the sites' discretion whether to perform a urine or serum pregnancy test. Enrollment is not contingent upon results. However, if a subject has a positive test result, it will be at the investigators discretion to weigh the risks verses benefits for the subjects continued participation. If the investigator decides to discontinue the study drug, please refer to Section 4.5.

#### **7.2.3.6      Electrocardiography**

ECG should be collected after the subject has been in a supine position for at least 5 minutes.

If abnormal results are observed, the investigator will assess clinical significance and determine whether the results should be recorded as an AE.

ECGs should be collected at the timepoints noted in Table 1.

#### **7.2.3.7      Modified Rankin Scale (MRS)**

The MRS is a commonly used 6-point scale for measuring the degree of disability or dependence in the daily activities of people who have suffered a stroke or other causes of neurology disability. The MRS should be assessed at the timepoints noted in Table 1.

#### **7.2.3.8      Full Outline of UnResponsiveness (FOUR) Score**

The FOUR Score is a clinical grading scale in the assessment of patients with impaired level of consciousness. The FOUR Score is a 17-point scale (with potential scores ranging from 0-16). Decreasing FOUR Score is associated with worsening levels of consciousness. The FOUR Score assesses four domains of neurological function: eye responses, motor responses, brain stem reflexes, and breathing pattern. The FOUR Score should be collected at the timepoints noted in Table 1.

#### **7.2.4      Others**

##### **7.2.4.1      Clinical Pharmacology Blood Sample Collection and Handling Procedures**

Blood samples will be collected at the times specified in Table 1. The sponsor's expectation is that the investigator will ensure that every effort is made to collect all pharmacokinetic blood samples at the precise protocol scheduled time. Pharmacokinetic blood collection must not deviate from the nominal collection time set forth in the protocol by more than  $\pm 5$  minutes from samples drawn within 4 hours post study drug initiation or by more than  $\pm 60$  minutes for samples

drawn beyond 4 hours post study drug initiation. Samples drawn outside these parameters will be considered a protocol deviation.

Venous blood samples (2 mL) will be drawn from indwelling catheters or by direct venipuncture into K2EDTA Vacutainer® tubes (lavender top), capped, mixed by inversion ( $\times 10$ ), and chilled immediately on crushed ice. If using indwelling catheters, they should be kept patent with isotonic saline and the saline should be withdrawn (1 mL) and discarded before the blood sample is taken. Use of topical anesthesia to reduce the pain of an indwelling catheter is permitted and, if used, must be documented as a concomitant medication. If venous blood sample collection is not possible an arterial sample may be collected. The type of sample will be recorded in the source documents and eCRF.

If study drug is administered via central access, the PK sample cannot be collected from any central access ports. If study drug is administered via venous access, the PK sample must be collected via the contra-lateral arm of the study drug arm. The location of study drug access and location of PK sample collection should be documented in the subject's source. If the PK sample cannot be collected due to poor venous access and the study drug infusion site is the only viable option, the specimen should not be collected and the reason for non-collection documented in the subject's source.

Details regarding sample collection, processing, storage, and shipment to the bioanalytical vendor are described in the Biospecimen Manual. The freezer temperature where these samples are stored must be controlled, monitored, and recorded during the storage period until the samples are shipped on dry ice to Quest Pharmaceutical Services for analysis. The study monitor must be notified of any temperature excursions.

#### **7.2.4.2      Shipment of Plasma Pharmacokinetic Samples**

Unless agreed upon by the sponsor, within approximately 1 week after subjects complete the in-patient follow-up day, the site will ship the primary plasma samples to QPS. Upon notification of receipt of the primary samples by QPS, the backup samples will be shipped to the bioanalytical laboratory. Refer to the Biospecimen Manual for details regarding specimen shipping.

#### **7.2.4.3      Plasma Drug Assay Methodology**

Plasma concentrations will be measured using the most current validated liquid chromatography with tandem mass spectrometry (LC/MS/MS) method. Other metabolites may be monitored or quantitated as appropriate. Raw data will be stored in the archive of the designated bioanalytical laboratory.

##### **7.2.4.3.1    Cerebral Spinal Fluid (CSF)**

If a subject has a lumbar puncture for the collection of CSF per investigator's discretion as part of their care and there is adequate volume, a sample will be aliquoted for future analysis of ganaxolone. If multiple lumbar punctures are performed, a sample from each puncture is requested. If not collected or not enough CSF is collected to provide a sample for the study, a sample will not be required.

Details regarding sample collection, processing, storage, and shipment to Bioanalytical vendor are described in the Biospecimen Manual. The freezer temperature where the samples are stored must be controlled, monitored, and recorded during the storage period until the samples are shipped on dry ice to Bioanalytical vendor for future analysis. The study monitor must be notified of any temperature excursions.

#### **7.2.4.4 Neurosteroid Blood Sample Collection and Handling Procedures**

Blood samples will be collected at the times specified in Table 1. Venous blood samples (2.5–6.0 mL) will be drawn into K2EDTA Vacutainer® tubes (lavender top), capped, mixed by inversion (×10), and chilled immediately on crushed ice. If using indwelling catheters, they should be kept patent with isotonic saline and the saline should be withdrawn (1 mL) and discarded before the blood sample is taken. Use of topical anesthesia to reduce the pain of an indwelling catheter is permitted and, if used, must be documented as a concomitant medication.

If study drug is administered via central access, the neurosteroid sample cannot be collected from any central access ports. If study drug is administered via venous access, the neurosteroid sample must be collected via the contra-lateral arm of the study drug arm. The location of study drug access and location of neurosteroid sample collection should be documented in the subject's source. If the neurosteroid sample cannot be collected due to poor venous access and the study drug infusion site is the only viable option, the specimen should not be collected and the reason for non-collection documented in the subject's source.

If venous blood sample collection is not possible an arterial sample may be collected. The type of sample will be recorded in the source documents and eCRF.

Details regarding sample processing, storage, and shipment to the bioanalytical storage/laboratory vendor are described in the Biospecimen Manual. The freezer temperature where the samples are stored must be controlled, monitored, and recorded during the storage period until the samples are shipped on dry ice to the bioanalysis storage/laboratory vendor. The study monitor must be notified of any temperature excursions.

Specific collection times can be found in Table 1.

**Table 4: Volume of Blood to Be Drawn from Each Subject**

Assessment		Sample Volume (mL) a	Number of Required Collection Timepoint Samples	Number of Variable Collection Timepoint Samples	Total Volume (mL)
Safety b	Biochemistry (with indwelling catheter)	8.5	6	2	51-68
	Hematology	4.0	6	2	24-32
	Coagulation	5.1	6	2	30.6-40.8
	IV AEDs	7.5	6	5	45-82.5
Pharmacokinetic samples (with indwelling catheter) c		3.0	9	4	27-39
Neurosteroid samples (with indwelling catheter) c		7.5	2	0	15
Arterial blood gas (for intubation only) b		1.0	0	1	1
Total mL					192.6-278.3

- a. If a catheter is used, the first milliliter (mL) collected is to be discarded, then the required volume is collected into the appropriate tube for the assessment. This additional 1 mL has been added the biochemistry, pharmacokinetic, and neurosteroid collections noted in the table. This assumes the hematology, coagulation, and AED samples will be collected at the same times as the biochemistry samples. The collection volume for coagulation testing at sites ranged from 2.7mL to 7.5.0mL, as such the median volume of 5.1mL was used for the table calculation.
- b. See Table 1 for a full sample collection list. There are required collection timepoints for all subjects and variable collection timepoints that only apply in specific situations. The two different types have been separated in the table to show the maximum and minimum number of sample collections for a subject.
- c. Blood samples for pharmacokinetic and neurosteroid analysis will be collected as noted in Table 1. Venous or arterial samples are acceptable.

**Table 5: Volume of Blood to Be Drawn from Each Subject (Pediatric Hospital Sample Volumes)**

Assessment		Sample Volume (mL) a	Number of Required Collection Timepoint Samples	Number of Variable Collection Timepoint Samples	Total Volume (mL)
Safety b	Biochemistry (with indwelling catheter)	2.0	6	2	12-16
	Hematology	1.0	6	2	6-8
	Coagulation	1.0	6	2	6-8
	IV AEDs	1.0	6	5	6-11
	Pharmacokinetic samples (with indwelling catheter) c	3.0	9	4	27-39
	Neurosteroid samples (with indwelling catheter) c	2.5	2	0	5
	Arterial blood gas (for intubation only) b	1.0	0	1	1
Total mL					62-88

a. If a catheter is used, the first milliliter (mL) collected is to be discarded, then the required volume is collected into the appropriate tube for the assessment. This additional 1 mL has been added to the biochemistry, pharmacokinetic, and neurosteroid collections noted in the table. This assumes the hematology, coagulation, and AED samples will be collected at the same times as the biochemistry samples.

b. See Table 1 for a full sample collection list. There are required collection timepoints for all subjects and variable collection timepoints that only apply in specific situations. The two different types have been separated in the table to show the maximum and minimum number of sample collections for a subject.

c. Blood samples for pharmacokinetic and neurosteroid analysis will be collected as noted in Table 1. Venous or arterial samples are acceptable.

During this study, it is expected that some sites (e.g., children's hospitals) will collect smaller volumes of blood from subjects per their local laboratory standards. The ranges in Table 4 and Table 5 reflect the possible range for adult and child versus a child-only hospital. The total blood volume could be as low as approximately 62 mL for pediatric-only versus 192.6 mL for other hospitals and up to approximately 88 mL for pediatric-only and 278.3 mL for other hospitals.

As noted in Table 1, several of the collection points are considered optional; however, to provide the most conservative estimate of the blood volume drawn, these option collections have been included in Table 4 and Table 5.

Note: The amount of blood to be drawn for each assessment is an estimate. The amount of blood to be drawn may vary according to the instructions provided by the manufacturer or laboratory for an individual assessment. When more than one blood assessment is to be done at a single timepoint/period, if they require the same type of tube, the assessments may be combined.

## 8. ADVERSE AND SERIOUS ADVERSE EVENTS ASSESSMENT

### 8.1 Definition of Adverse Events, Period of Observation, Recording of Adverse Events

An AE is any untoward medical occurrence in a clinical investigation subject who has been administered a pharmaceutical product; it does not necessarily have a causal relationship with this treatment. An AE can therefore be any unfavorable and unintended sign (including an abnormal laboratory finding), symptom, or disease temporally associated with the use of a medicinal (investigational) product, whether or not related to the medicinal (investigational) product.

As this study allows for pre-consenting of subjects, all AEs will be collected from the time of first dose of study drug until the defined follow-up period stated in Section 7.1.3. Where possible, a diagnosis rather than a list of symptoms should be recorded. If a diagnosis has not been made, then each symptom should be listed individually. All AEs should be recorded on the appropriate AE pages in the eCRF and in source documents. In addition to untoward AEs, unexpected benefits outside the study drug indication should also be recorded on the AE eCRF page.

All AEs must be followed for the durations described below. For AEs followed to closure, this indicates that an outcome is reached, stabilization is achieved (the investigator does not expect any further improvement or worsening of the event), or the event is otherwise explained. When appropriate, medical tests and examinations are performed so that resolution of event(s) can be documented.

For subjects who:

- a. Have 2 days of treatment which includes a 12-hour study drug taper, all adverse events will be collected through the in-patient follow-up day. During the weekly follow-up visits only, ongoing AEs and new AEs assessed by the investigator to be related to study drug will be recorded. All SAEs regardless of relationship to study drug will be recorded from the time of 1st dose through the last follow-up visit/contact.
- b. Stop study drug administration without a study drug taper but continue with the follow-up visits, all adverse events will be collected through the in-patient follow-up day. During the weekly follow-up visits, only ongoing AEs and new AEs assessed by the investigator to be related to study drug will be recorded. All SAEs regardless of relationship to study drug will be recorded from the time of 1st dose through the last follow-up visit/contact. Additionally, AEs of UTI, hospital-acquired/ventilator-associated pneumonia, MI, sepsis from any source, critical illness myopathy/neuropathy and significant hypotension requiring vasopressor support will be recorded as AEs regardless of relatedness.
- c. Early terminate from the study, prior to discontinuation as much information as is available should be recorded on any on-going AEs/SAEs and AEs/SAEs that may have led to the early termination.

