### **Methodology:**

This is a double-blind, randomized, placebo-controlled study to evaluate the safety, tolerability, efficacy of adjunctive ganaxolone IV solution in subjects with SE. This study will start with a small open-label group to confirm that the dose selected will achieve a potentially therapeutic exposure (bolus plus continuous infusion) to stop SE. The dose selected for Day 2 is designed to provide a stable plasma concentration to maintain status cessation. If needed, doses in the open-label group portion of the study may be adjusted based on the dosing and pharmacokinetic/safety profile from the subject's enrolled.

As previously described, the study drug will be added to the standard of care from the time that the first 2nd line IV AED, administered at an appropriate dose and duration to show efficacy, has failed and the second 2nd line IV AED is medically indicated during the treatment of SE. Study drug must be administered with the 2nd line IV AED treatment and should be initiated as close to the initiation of the second 2nd line IV AED as possible.

Potential subjects are anticipated to be identified in the emergency department and/or hospital in-patient or intensive care units.

Upon identification, subjects will be administered consent/assent and then screened for inclusion/exclusion criteria prior to receiving study drug as adjunctive therapy via continuous IV infusion, followed by a 12-hour study drug taper. As soon as the study drug administration is completed (with or without taper), subjects will have a 24-hour in-patient follow-up day and then follow-up visits/contacts at weeks 2, 3, and 4. For subjects who have the 12-hour study drug taper, the in-patient follow-up day starts as soon as the 12-hour study drug taper is complete. If the infusion rate becomes too low to sustain the infusion line, it can be discontinued at that point and the subject will progress into the in-patient follow-up day. For subjects where there is no study drug taper the in-patient follow-up day starts as soon as the study drug administration is discontinued. These subjects will continue with the week 2, 3, and 4 follow-up visits.

If the subject remains hospitalized, the week 2, 3, and 4 visits will be done in-person. If the subject has been discharged, these visits may be conducted via telephone call. However, it is recommended

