- c. During the weekly follow-up visits, only ongoing AEs and new AEs assessed by the investigator to be related to study drug will be recorded and the concomitant medications associated with these AEs.

- d. In addition, during the weekly follow-up visits, AEs of urinary tract infection (UTI), hospital-acquired/ventilator-associated pneumonia, myocardial infarction (MI), sepsis from any source, critical illness myopathy/neuropathy, significant hypotension requiring support of vasopressors will be recorded regardless of relatedness. Associated concomitant medications for these AEs will not be recorded.
- e. All SAEs regardless of relationship to study drug and their associated concomitant medications will be recorded from the time of study drug initiation through the last follow-up visit/contact.
- f. For subjects who early terminate from the study, prior to discontinuation as much information as is available should be recorded for ongoing AEs/SAEs, new AEs/SAEs and their associated concomitant medications, especially those that may have led to the early termination.

For some of the concomitant medications only the highest dose administered will be required in the eCRF. Reference the eCRF Completion Guidelines for guidance.

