### **Maximum Duration of Subject Involvement in the Study:**

- Screening could be as short as a few minutes and as long as approximately 24 hours prior to the initiation of study drug. The screening period is from the time parent/guardian/LAR consent/assent is obtained to immediately prior to study drug initiation.
- The planned duration of adjunctive treatment is 2 days which includes a 12-hour study drug taper.
- There will be an in-patient follow-up period after the study drug administration is completed. The in-patient follow-up period starts at the time of study drug discontinuation; either at the end of the taper or if the study drug administration is stopped without a taper. The follow-up period consists of a 24 hour in-patient follow-up day and 3 weekly visits. These weekly visits can be performed as an in-person visit if the subject is still in the hospital, or as a telephone call if the subject has been discharged. However, it is recommended that discharged subjects return so at least one of these visits will be conducted in-person.
- In total, subjects will be followed for approximately 4 weeks.

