### **6.2.3 Dosing**

Total adjunctive ganaxolone IV solution therapy infusion treatment is planned to be 2 days which includes a 12-hour study drug taper. All subjects will have an ~3-minute bolus dose with a continuous infusion at the rate of 20-80 mg/hour, and a 12-hour study drug taper (see Table 2 and 3 for details). Once study drug administration is started it should be delivered for 2 days (48 hours) which includes a 12-hour taper.

Study drug should be administered, ideally, through a dedicated (peripheral or central) IV line. These infusion parameters result in daily doses of ganaxolone of  $\leq$  830 mg/day and Captisol of  $\leq$  50 g/day as agreed upon with the FDA. Based on PK modeling, it is predicted that maximum concentrations of ganaxolone should remain within 1,000 ng/mL during infusion, but some variability is expected due to, for example, differences in subjects' weight. Note, at any time, the infusion rate of the ongoing administration may be decreased for safety reasons, see Dose Adjustments and Interruptions section below for more information.

Note, pharmacokinetic data from study 1042-0405 in healthy volunteers showed that a bolus infusion of 30 mg ganaxolone over 5 minutes led to transient peak concentration levels ( $C_{max}$ ) above 1,000 ng/mL (maximal observed  $C_{max}$  was 1,850 ng/mL) with no safety concerns. Infusion of 30 mg/hour for 1 hour and 20 mg/hour for 4 hours led to concentrations of 258 and 215 ng/mL, respectively, again without any safety concerns (see Section 1.2 Product Background and Clinical Information).

During the open-label group, based on the safety, efficacy, and pharmacokinetic data from the ongoing study, the infusion parameters in subsequent subjects may be adjusted to maximize the safety and efficacy of study subjects. If the infusion parameters are amended, the new infusion parameters will not exceed the daily limit of 50 g/day Captisol ( $\leq$  830 mg/day ganaxolone) as agreed upon with the FDA. The revised infusion parameters will be communicated to Clinical Sites in a Protocol Administrative Change Memo and kept in the study and site files.

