4.9.1 Adverse Events

Adverse events are coded using the MedDRA dictionary, Version 20.1 or higher, and are categorized by system organ class (SOC) and preferred term (PT). Only treatment emergent adverse events are included in the summary tabulations. All adverse events are included in the data listings.

To allow differentiation as to which study period an Adverse Event occurred, two categories are defined based upon onset date. Adverse Events that had onset dates prior to the first dose of study medication are considered "prior". Adverse events with onset dates on or after the first dose of study medication and up to end of follow-up period are considered "on-therapy" or equivalently "treatment emergent". Adverse events with an onset date prior to the first dose of study medication but worsens after treatment starts are considered a treatment emergent AE.

Overall summary of Treatment-emergent adverse events (TEAE) will be provided. The TEAEs will be summarized by MedDRA System Organ Class (SOC) and preferred term (PT), and by group (by cohort and overall). Treatment-emergent adverse events will further be summarized by severity and relationship to treatment medication. Treatment-emergent Serious Adverse Events (SAE) and AEs leading to discontinuation of study drug will also be summarized by SOC, PT, and group (by cohort and overall).

Adverse events and serious adverse events will be listed.

Deaths will be listed and summarized by group (by cohort and overall).

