- ^u Status Epilepticus and Seizure Questions should be assessed at 60 minutes, 2 hours, 48 hours post-dose, and on the 24-hour post-taper follow-up day, and at weeks 2, 3, and 4. Also collect at the time of study drug termination if there is no taper and something has changed since the last collection timepoint, and at the time of early termination, when the decision to stop study drug administration is made and as close as possible to the end of the study drug administration.
- ^v AEs and concomitant medications will be collected throughout the study; non-direct questioning will occur. The collection requirements will differ depending on the subject's treatment progression as defined here: 1. For subjects who have 2-4 days of treatment with an 18-hour study drug taper, all adverse events and associated concomitant medications will be collected through the 24-hour post-taper follow-up visit. During the weekly follow-up visits only, ongoing AEs and new AEs assessed by the investigator to be related to study will be captured along with their associated concomitant medications. 2. For subjects who stop study drug administration without a taper but continue with the follow-up visits, all adverse events will be collected through the 24-hour post-taper follow-up visit, with their associated concomitant medications. During the weekly follow-up visits only, ongoing AEs and new AEs assessed

by the investigator to be related to study will be captured, with their associated concomitant medications. 3. For subjects who early terminate from the study, prior to discontinuation as much information as is available should be recorded on any on-going AEs/SAEs and AEs/SAEs with their associated concomitant medications, especially those that may have led to the early termination. 4. All SAEs regardless of relationship to study drug will be recorded from the time of 1st dose though the last follow-up visit, with their associated concomitant medications.

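### Full adverse-event recording ends 24 h after study drug stops, so its length follows the efficacy outcome and crude percentages for one class of AEs are not comparable between cohorts

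*Protocol*

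**What the plan says.** **Length of full recording.** For subjects treated for 2 days with taper, Protocol 8.1 item a says that "all adverse events will be collected through the in-patient follow-up day". Item b sets the same limit for those who stop "without a study drug taper but continue with the follow-up visits, all adverse events will be collected through the in-patient follow-up day". Synopsis item 17a and Table 1 footnote u(1) agree.

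**What that day is.** The synopsis, under maximum duration, states: "The follow-up period consists of a 24 hour in-patient follow-up day and 3 weekly visits". Its start depends on when drug ends: "For subjects where there is no study drug taper the in-patient follow-up day starts as soon as the study drug administration is discontinued" (synopsis, Methodology; repeated in 3.1). For completers, Protocol 6.2.3 states: "Once study drug administration is started it should be delivered for 2 days (48 hours) which includes a 12-hour taper".

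**Link to efficacy.** Under Protocol 5.2.2 and 6.2.3, progression to an IV anesthetic for seizure suppression ends study drug without a taper, and the subject stays in follow-up. Under 9.7.1, needing an IV anesthetic within 24 h of initiation is failure on the primary endpoint.

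**After that day.** At the weekly visits "only ongoing AEs and new AEs assessed by the investigator to be related to study drug will be recorded" (synopsis item 17c). All SAEs are recorded to the last contact. Six named AEs (such as urinary tract infection, pneumonia and sepsis) are recorded whatever their relatedness.

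**Analysis.** Protocol 9.8 gives counts and percentages by treatment group. SAP 4.4 uses the number of subjects as denominator. SAP 4.9.1 says: "Adverse events with onset dates on or after the first dose of study medication and up to end of follow-up period are considered" treatment emergent, and tabulates these by cohort and overall. Footnote v of the SAP's schedule carries the same recording limit: "all adverse events will be collected through the 24-hour post-taper follow-up visit, with their associated concomitant medications".

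**The concern.** The period in which every AE must be recorded is set by the time study drug stops, and early stopping is often the efficacy failure itself. A cohort with more early escalations is watched in full for less time. The TEAE definition runs to the end of follow-up for everyone, so a reader of the tables would assume even ascertainment. Neither document plans a common cut-off or any allowance for time under full recording. Between the open-label dose cohorts, a difference in recorded AEs could therefore partly reflect who stopped early. The same would apply between arms if the rule were used in the double-blind comparison that the protocol describes.

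**Working it through.** **1. The plan's own duration.** Infusion in Protocol 6.2.3: 2 + 10 + 12 + 12 = 36 h. Adding the 12 h taper gives 48 h, as stated.

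**2. Full-recording windows.** Completer: 48 + 24 = 72 h. Stop without taper at hour t: t + 24 h.

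| Stop time t | Window | 72 / window |
|---|---|---|
| near 0 h | just over 24 h | 3.0 |
| 2 h | 26 h | 2.77 |
| 6 h | 30 h | 2.4 |
| 12 h | 36 h | 2.0 |
| 24 h | 48 h | 1.5 |

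Protocol 6.2.3 foresees stops before 2 h, so the floor is just over 24 h. Primary-endpoint failures occur between 0 and 24 h, hence windows up to 48 h (taking drug to stop when the anesthetic starts). Under the SAP's schedule (48 to 96 h of infusion, 18 h taper), a completer has 48 + 18 + 24 = 90 h to 96 + 18 + 24 = 138 h.

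**3. Illustration of size.** The documents give no AE hazards, so these are assumptions: an equal constant hazard in all subjects, every failure stopping at the same t, everyone else completing, and every AE after t + 24 h lost. Response rates are 60% and 40%, from a row of Protocol Table 7.

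- Risk in a window of w hours = 1 − (1 − p72)^(w/72), where p72 is the 72 h risk.
- p72 = 50%, t = 6 h, w = 30 h: 1 − 0.5^(30/72) = 25.1%.
- 60% response: 0.6 × 50% + 0.4 × 25.1% = 40.0%.
- 40% response: 0.4 × 50% + 0.6 × 25.1% = 35.1%.
- Artefact: about 5 points.
- For p72 from 30% to 70% and t from 3 to 12 h, the artefact is 2.7 to 6.7 points.

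**4. Relaxing the assumptions.**

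- *Only part of the AEs is lost.* If half the hazard lies in classes still recorded (assumption), the failure's effective window in the example is 30 + 0.5 × 42 = 51 h. The risk is 1 − 0.5^(51/72) = 38.8%, and the artefact is 0.2 × (50% − 38.8%) = 2.2 points.
- *Failures have a higher hazard.* The recorded difference cancels when the hazard in failures is 72/(t + 24) times that in completers: 2.77 at t = 2 h, 2.4 at 6 h, 1.5 at 24 h. Above that it reverses.
- *Cancelling is not the same as no distortion.* With p72 = 30% in completers, t = 2 h and a 2.77-fold hazard, the failures' 72 h risk is 1 − 0.7^2.77 = 62.8%. True incidence is then 0.6 × 30% + 0.4 × 62.8% = 43.1% against 0.4 × 30% + 0.6 × 62.8% = 49.7%. Both groups are recorded as 30%.

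**5. Recording rules side by side.**

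- Protocol 7.2.3.3 and the opening of 8.1 describe AE collection through follow-up without restriction. Items a and b of 8.1 restrict it after the in-patient day.
- Section 8.1 lists the six named AEs only under item b (no taper). Synopsis item 17d and Table 1 footnote u(4) apply them to all subjects. Read literally, 8.1 gives early stoppers more recording of these six events than completers, the opposite direction to step 2.
- Footnote v of the SAP's schedule has no such list, so for subjects recorded under it the affected class includes those events too.

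**The case against.** The strongest case against is that little is at risk here. SAP Section 1 moves the double-blind phase to a separate phase 3 study, and SAP 5.1 says this study closed before reaching it. No inferential test is planned, and listings of all AEs and all doses are. That stands, and it sets the severity.

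A reader might infer that AE rates in general are biased. The documents do not support this: SAEs, ongoing AEs and related AEs continue to the last contact whenever drug stopped. One qualification is that the guidance table in Protocol 8.1.2 reserves related for events that other therapies cannot explain. After escalation, sedation or hypotension may plausibly be ascribed to the anesthetic, so the relatedness route may be weakest in the subjects with the shortest window.

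A reader might also infer that the cohort or arm with more failures must look safer, or that ganaxolone would show a spurious excess over placebo. That needs the equal constant hazard, which is doubtful. Protocol 2.1 links anesthetics to hypotension and cardiopulmonary depression, which would raise the hazard in failures. The infusion rate is highest in the first 2 h, so AEs may cluster early, which would shrink the gap. The direction is therefore open; the unequal recording is not.

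Finally, a window tied to the last dose is a legitimate design choice. It needs an analysis that respects it, and none is planned.

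**Conclusion.** The point holds in limited form. Full AE recording lasts just over 24 h to 48 h for primary-endpoint failures and 72 h for completers (90 to 138 h under the SAP's schedule). This follows from the text and needs no assumption beyond drug stopping at escalation. For new, non-serious AEs judged unrelated and outside the six named events, crude TEAE percentages are not comparable between cohorts, and would not be between arms.

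The size is not known. The 2.7 to 6.7 points are an upper-leaning illustration that rests on equal constant hazards and on every later AE being lost. They are not an estimate for this study, in which no placebo comparison was run. Severity is low: descriptive cohort tables are affected, and no test or decision rule is.

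**What to change.** 1. **Recording, for any further subjects and for the double-blind comparison.** In Protocol 8.1 items a and b, synopsis item 17a and Table 1 footnote u(1), set the end of full AE recording as *the later of the end of the in-patient follow-up day and 72 hours after study drug initiation, whether or not study drug has been stopped*. This gives failures and completers the same 72 h under the 48 h regimen.

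2. **Analysis, for subjects already treated.** In SAP 4.9.1, add a TEAE table by cohort limited to the first 24 h after initiation (by calendar day where onset time is missing). All subjects who remain in the study share that window under either schedule. Footnote the all-TEAE tables with the unequal recording windows. Events per subject-hour should not be the main remedy: it also assumes a constant hazard, and if AEs cluster early it would inflate the rate in short-window subjects.

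3. **Consistency.** Reconcile Protocol 7.2.3.3 and the opening of 8.1 with 8.1 items a and b on the end of AE collection. Reconcile 8.1 items a and b with synopsis item 17d and footnote u on who has the six named AEs recorded.

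**Cost.** Up to about 72 − 24 = 48 h of extra chart-based AE entry for the earliest stoppers, one extra table, and text edits. The 24 h table says nothing about later events, so it supplements the all-TEAE tables and does not replace them.
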